2 weeks post-mCM treatment follow-up			
8	Phone	Questionnaires; equipment return; treatment adherence measures	\$50 for equipment return
3 months after Session 1			
9	Phone/Lab	Questionnaires; return to lab and provide a saliva sample if abstinence reported	\$25 for assessment; \$50 for saliva sample
6 months after Session 1			
10	Phone/Lab	Questionnaires; return to lab and provide a saliva sample if abstinence reported	\$25 for assessment; \$50 for saliva sample
TOTAL COMPENSATION POSSIBLE			\$1098

Once a participant reports to the laboratory to begin the study, the study staff member obtaining consent will explain the study in detail, provide the participant with an IRB-approved written consent form explaining the procedures and risks, and answer any questions. The initial consent process and documentation takes place in a quiet, private office at DUMC (Hock Plaza space), and participants are given the chance to thoroughly read the consent prior to participation. Participants are given a copy of the signed informed consent form, and are given phone numbers to call if they have additional questions about the consent form or the research, if they have any problems during the study, or if they have questions about participating in research studies in general. No study procedures will begin until informed consent has been obtained.

After providing informed consent, potential participants will provide a breath sample to assess CO level, and will complete measures (see Measures section herein) regarding mood, exercise and smoking history, and sociodemographic data. Urine samples will also be used to screen for illicit drug use (to document use). Because the study drugs are each Category C drugs, urine pregnancy tests will also be completed for women of childbearing potential. We have developed a short interview for female participants; this interview will help us determine which female participants must have a urine pregnancy test, and when the test should be done. Female participants of childbearing potential who are not pregnant must agree to use appropriate

contraception during the course of the study, and to notify study staff if they become pregnant during the study.

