Post-Treatment Session and 3-Month and 6-Month Follow-Up. To eliminate the burden of travelling to study appointments for assessments, telephone surveys will be conducted at the end of the mCM/mobile assessment phase. At that phone visit, participants will complete measures (read aloud by study coordinator) about treatment acceptability, smoking, medication adherence, self-efficacy to quit/remain quit, and physical activity.

Participants will be contacted by phone at 3- and 6-months post-screening visit. During the phone visit, participants will complete measures (read aloud by study coordinator) about smoking, medication adherence, self-efficacy to quit/remain quit, and physical activity. If participants report smoking abstinence at the 3 and 6-month follow-ups, they will be asked to come to the laboratory to provide a saliva sample and CO reading to bioverify smoking abstinence. If any participant is unable to come to the laboratory, he/she will be asked to provide a saliva sample by mail. When saliva is collected by mail, participants are sent instructions, saliva vials, a brief tobacco use assessment (that includes use of nicotine replacement therapies in the prior week), and a postage-paid padded envelope for returning the sample to the study coordinator. At each time point, any participant who provides a saliva sample will be paid \$50. All sample identification will be with an assigned study number rather than patient identifiers. Saliva samples will be mailed to Salimetrics, LLC for cotinine assay (see "Smoking-Cessation Outcome Measures and Biochemical Verification" herein).

Participant Reimbursement. Participants who drop out will receive partial reimbursement for the time and effort they devote to the study. Because monetary reinforcement is an essential part of the intervention we are studying, participants will receive payments as reinforcers during treatment in addition to payments they receive to compensate for their time and effort on the study. Participants are paid: 1) \$100 for completion of the screening visit and mCM training; 2) up to \$798 for mCM; 3) \$50 for equipment return at the end of treatment; 4) \$25 each for the assessments at 3- and 6-month follow-up; and 5) \$50 (each) for provision of saliva samples at 3- and 6-month follow-up. Participants could be paid up to \$1098 for their complete participation.

Study Measures

Table 2 outlines measures to be given at each time point in the study.

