Table 2. Study Measures and Schedule of Administration

	Baseline	Weekly	PT*	3 Months	6 Months
Background Variables					
Demographics	X				
Fagerström Test of Nicotine Dependence	X		X	X	X
Minnesota Nicotine Withdrawal Scale			X	X	X
General Smoking History Questionnaire	X				
NRT & Bupropion Contraindications	X				
Stanford 7-Day Physical Activity Recall	X		X	X	X
Intrapersonal Variable					
Short Form 36 Health Survey	X		X	X	X
Global Self-Efficacy for Quitting Smoking	X		X	X	X
Readiness-to-Change Questionnaire	X		X	X	X
NRT & Bupropion Self-Efficacy	X		X	X	X
Physical Activity Self-Efficacy	X		X	X	X
Social Support	X		X	X	X
Positive and Negative Affect	X	X	X		
Physical Vigor	X	X	X		
Process Measures					
Treatment-Acceptability Survey			X		
Use of Smoking-Cessation Aids		X	X	X	X
Morisky Adherence Questionnaire		X	X	X	X
Outcome Measures					
Prolonged Abstinence: 7-day		X	X	X	X
Prolonged Abstinence: 30-day				X	X
Quit Attempts			X	X	X
Timeline Follow-Back-Quit Attempts			X	X	X
Steps (Assessed by Step-Tracker)	X	X	X		

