Smoking-Cessation Outcome Measures and Biochemical Verification. Our choice of primary and secondary smoking endpoints follows recommendations by the Society of Research on Nicotine and Tobacco (SRNT; Hughes et al., 2003). Self-reported and bio-verified prolonged abstinence at the 3- and 6-month follow-ups will be the primary endpoints. Prolonged abstinence will exclude tobacco use in the first 2 weeks following the quit date (Hughes et al., 2003). Self-reported prolonged abstinence will be verified by cotinine assay. CO and saliva samples will be collected from participants who report prolonged abstinence at each follow-up. Saliva samples will be sent to the Duke University Nicotine Research Program to be analyzed for the presence of cotinine using a standard cut point of 10 ng/ml to determine abstinence. A blind sample of 5% will be rerun to assure test accuracy of saliva samples. Secondary smoking outcomes will include 7- and 30-day point prevalence abstinence at each assessment, where abstinence is defined as no tobacco use in the prior 7 or 30 days respectively. Additionally, participants will be asked if they have made one or more quit attempts in each follow-up period using a time-line follow back method (Lewis-Esquerre et al., 2005). We have recent experience using this method to assess daily smoking behavior (Carpenter et al., 2015).

Potential Risks

There is a risk of discomfort or distress in answering questions on the study measures. However, distress and discomfort related to questionnaire completion is usually temporary and well-tolerated. Risks also include discomfort related to quitting smoking. Quitting smoking may cause difficulty concentrating, poor sleep, increased appetite, anxious or depressed mood, and craving for cigarettes. Participants will be offered NRT, and there are risks associated with the use of NRT. Minimal risks associated with wearing a nicotine patch include skin irritation, dizziness, lightheadedness, increased heart rate or blood pressure, nausea or vomiting. If a participant indicates a contraindication to NRT (e.g. uncontrolled hypertension), medical clearance for NRT will be sought from the participant's primary care physician and/or the study physician. If a participant with a seizure disorder, history of or current hepatitis and/or cirrhosis, renal

impairment, and/or uncontrolled diabetes wishes to enroll in the study, he/she will not receive contraindicated medications.

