Self-reported and bioverified prolonged abstinence from smoking at the 3 and 6-month follow-up will be the primary end-point. Prolonged abstinence will exclude tobacco use in the first two weeks following the quit date to give participants time to achieve initial abstinence (Hughes et al., 2003). Self-reported prolonged abstinence will be verified by cotinine assay, a metabolite of nicotine in the saliva. Saliva samples will be collected from participants who report prolonged abstinence at each follow-up. They will be mailed to Salimetrics LLC for saliva cotinine assays. Saliva samples will be analyzed for the presence of cotinine using a standard cut point of 10 ng/ml to determine abstinence. A blind sample of 5% will be run again to assure test accuracy of saliva samples. Secondary smoking outcomes will include 7- and 30-day point prevalence abstinence at each assessment, where abstinence is defined as no tobacco use in the prior 7 or 30 days, respectively.

Data Analyses

Descriptive statistics will be used to summarize all study variables, including smoking history and current use, nicotine-dependence level, self-efficacy, readiness to change, and social support. For continuous variables, means, standard deviations, ranges, and histograms will be generated. For categorical variables, frequencies and proportions will be generated. Individual and mean trajectory plots of the longitudinal outcome variables will be constructed to understand their general trends over time (i.e., post-treatment, 3- and 6-month follow-ups). We will examine all variables to determine if parametric distributional assumptions (e.g., normality for the continuous variables) are valid. Variables not meeting distributional assumptions will either be transformed or modeled using non-parametric or semi-parametric methods (e.g., quasi-likelihood methods; McCullagh & Nelder, 1989). In order to describe the compliance/completion of the sample in terms of smoking-cessation aids and intervention completion, these variables will be summarized. In terms of descriptors for outcome measures, we will record number of quit attempts, quality of life, and number of weekly steps, and utilize time-line follow-back data to identify when participants may have lapsed. Potential covariates (e.g., age, gender, minority status) will be evaluated for inclusion in models. If any of these variables have a significant bivariate effect on treatment outcomes, they will be entered first in statistical models.

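### The 10 ng/ml cotinine rule behind the primary endpoint makes no provision for participants using nicotine replacement, and the 7- and 30-day outcomes use no sample result

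*Combined protocol and SAP*

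**What the plan says.** **Primary endpoint.** In Outcome Measurement and Biochemical Verification, self-reported prolonged abstinence "will be verified by cotinine assay, a metabolite of nicotine in the saliva", with 10 ng/ml as the cut point. Smoking-Cessation Outcome Measures and Biochemical Verification gives the same cut point. Neither section mentions nicotine replacement therapy (NRT).

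**NRT supplied.** Table 1 starts NRT at Session 4, the quit date. Pharmacotherapy for Smoking Cessation lists a nicotine patch, with no length given, and 8 weeks of gum or lozenge as rescue.

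**Secondary outcomes.** Both outcome sections name "7- and 30-day point prevalence abstinence at each assessment, where abstinence is defined as no tobacco use in the prior 7 or 30 days". No cotinine or CO condition is attached. Table 2 labels the first of these measures "Prolonged Abstinence: 7-day" and gives the 30-day row the same prefix.

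**Who is sampled.** Table 1, Sessions 9 and 10: "return to lab and provide a saliva sample if abstinence reported". The follow-up section says of participants who report smoking abstinence that "they will be asked to come to the laboratory to provide a saliva sample and CO reading to bioverify smoking abstinence". The Study Measures text says "CO and saliva samples will be collected from participants who report prolonged abstinence at each follow-up". The later outcome section says "Saliva samples will be collected from participants who report prolonged abstinence at each follow-up".

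**What is recorded about NRT.** The mailed saliva kit asks about NRT use in the prior week. Table 2 schedules smoking-cessation aids and the Morisky questionnaire at 3 and 6 months, and the follow-up phone visit covers medication adherence. The primary self-report adherence measure is days of NRT (and bupropion, if prescribed) used during the study period.

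**The concern.** Cotinine cannot tell nicotine from a cigarette apart from nicotine from a patch, gum or lozenge. Read literally, the 10 ng/ml rule fails someone who has stopped smoking but still uses the product the study gave them. The error runs one way: it lowers the primary endpoint, and it falls on participants who keep using their medication. If no rule is written beforehand, a positive cotinine in an NRT user will have to be resolved once results are known, which leaves the primary endpoint open to discretion.

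The secondary issue runs the other way. A 7- or 30-day report counts in full whether or not a sample exists and whatever it shows, so those rates can only equal or exceed a verified version.

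The protocol lists efficacy among the pilot's purposes and says the data will inform planning of a larger randomized trial. What is at stake is mainly the definition that is carried forward.

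**Working it through.** The plan gives no figure to reproduce here. The check places the NRT course against the follow-up visits, sizes one misclassification, and compares the sampling instructions.

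**1. When the NRT course ends**

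Inputs: Table 1 intervals (Session 1 to 2, 1-3 weeks; 2 to 3, 1 week; 3 to 4, 1 week); an 8-week course; follow-ups 3 and 6 months after Session 1. Assumptions: the gum or lozenge course starts on the quit date; 3 months is week 13 (or week 12); 6 months is week 26.

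- Quit date = (1 to 3) + 1 + 1 = weeks 3 to 5.
- Course end = 3 + 8 to 5 + 8 = weeks 11 to 13.

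| Visit | Visit week minus course end | Meaning |
|---|---|---|
| 3 months as week 13 | 13 - 13 = 0 to 13 - 11 = 2 | course ended 0-2 weeks before |
| 3 months as week 12 | 12 - 13 = -1 to 12 - 11 = 1 | from 1 week before to 1 week after |
| 6 months as week 26 | 26 - 13 = 13 to 26 - 11 = 15 | course ended 13-15 weeks before |

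Patch use cannot be placed, because no length is given.

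**2. Route to misclassification**

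A participant reports prolonged abstinence truthfully, still uses NRT, and gives saliva above 10 ng/ml. The cut point alone decides, so the participant is not counted as abstinent. The documents do not state what cotinine level NRT produces or how fast it clears. That current use can exceed 10 ng/ml is an assumption.

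**3. Size of one case**

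1/15 = 6.7 points; 1/10 = 10 points. As an illustration with assumed counts, 3 of 10 abstinent is 30%; if one is reclassified, 2 of 10 is 20%. The documents give no basis for the number of cases.

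**4. Data held against rules stated**

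| Item | Collected? | Used in classification? |
|---|---|---|
| CO at follow-up | Yes, at lab visits | No rule, and no follow-up cut point |
| Prior-week NRT use | Explicitly on the mailed form | No |
| Cessation aids, adherence | Yes, at 3 and 6 months | No |

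The only CO abstinence cut point in the plan is < 6 ppm, in Mobile CM Procedures, where it governs incentive payments.

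**5. Sampling instructions**

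| Section | Who | What |
|---|---|---|
| Table 1, Sessions 9-10 | reports abstinence | saliva |
| Follow-up section | reports smoking abstinence | saliva and CO (saliva only by mail) |
| Study Measures text | reports prolonged abstinence | CO and saliva |
| Outcome Measurement section | reports prolonged abstinence | saliva |

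Consider someone who smoked after the 2-week grace period, quit again, and has been abstinent for 7 or 30 days. The first two rows request a sample; the last two do not describe one. This takes later smoking to end prolonged abstinence, although the plan does not say how much later use does so. Under any of the four rows, the 7- and 30-day definitions make no use of the result.

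**The case against.** **The course is nominally over by the 3-month visit.** With 3 months as week 13, it has ended in every case. Misclassification then needs use beyond the course, patch use of unstated length, or cotinine that has not yet cleared. This stands, and is why the claim is that misclassification can happen, mainly at 3 months. A reader might infer a similar problem at 6 months, but a gap of 13-15 weeks does not support that unless patch or non-study NRT use continues.

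**NRT use is recorded.** A reader might infer that the plan is blind to it at lab visits. It is not: cessation aids, adherence and days of use are all collected. None is explicitly prior-week NRT use tied to the sample, and none enters the classification. What is missing is the rule.

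**Self-reported secondary outcomes are legitimate.** This stands. A reader might infer that the 7- and 30-day outcomes are wrongly defined, or that the four sampling instructions contradict each other. Neither follows. The definition given is a usable self-report one. The two outcome sections do not limit collection to prolonged abstainers, so sampling everyone who reports abstinence satisfies all four. The plan simply does not say so.

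**Payment for samples.** A reader might infer that the payment inflates abstinence, since "At each time point, any participant who provides a saliva sample will be paid" and a sample follows a report of abstinence. Everyone so paid has supplied the specimen that can contradict the report, so the documents show no bias from this.

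**Too small to matter.** An assumed 3 of 15 has an exact 95% interval of 4% to 48%, far wider than a one-person shift. This also stands. The gain is a definition fixed in advance, not a more precise pilot estimate.

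**Conclusion.** The main point holds. The cotinine rule for the primary endpoint has no provision for NRT, although the study supplies NRT and the 8-week course ends at about the 3-month visit. The effect is downward, by 6.7 points per person of 15 or 10 points per person of 10, for an unknown number of people. It rests on the Table 1 intervals, a course starting on the quit date, and the assumption that current NRT use can give cotinine above 10 ng/ml. The plan should be amended.

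The secondary point holds at lower severity: the sampling instruction needs one wording, the Table 2 labels are wrong, and the plan should say how samples bear on the 7- and 30-day outcomes. The documents support no estimate of over-reporting in those outcomes.

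**What to change.** **Primary endpoint**

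1. Ask about prior-week NRT use with every 3- and 6-month sample, at lab visits as well as by mail.
2. For a participant who reports NRT use and has cotinine above the cut point, classify by the CO reading from that visit. Fix the CO cut point before the first 3-month visit and write it into both outcome sections.
3. If there is no CO reading, as with a mailed sample, count the report as unverified.
4. Show the cotinine-alone result as a sensitivity analysis.

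**Secondary outcomes**

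5. Reconcile the four instructions: anyone reporting 7-day, 30-day or prolonged abstinence at 3 or 6 months is asked for saliva, plus CO at a lab visit.
6. At those visits report 7- and 30-day abstinence as self-reported (labelled unverified) and as confirmed by the sample. Count a missing sample as not verified.
7. Rename the two Table 2 rows as point prevalence abstinence.

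**Cost.** Wording, and one question at lab visits. The ceiling is 15 x 2 = 30 samples. The 5% blind rerun adds 0.05 x 30 = 1.5, so 1-2, making 31-32 assays; the assay price is not in the documents. Sample payments reach at most 30 x $50 = $1,500, already inside the plan's maximum per participant: 100 + 798 + 50 + 2 x (25 + 50) = $1,098.

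Reporting grows to 2 outcomes x 2 visits x 2 versions = 8 secondary rates, plus 2 visits x 2 versions = 4 primary rates. Twelve rates in 15 people should be presented as counts, without tests.

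**Downsides.** CO does not detect smokeless tobacco, and the exclusion covers only exclusive users of other nicotine forms, so dual users can enrol; hence step 4. Counting missing samples as unverified lowers the confirmed rate if true abstainers do not return them; hence the self-reported rate beside it.
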